1 BACKGROUND INFORMATION

1.1 Anti-PD1 Antibody

The anti-PD1 antibody nivolumab (OPDIVO, BMS®) has become the new standard of care after first-line platinum doublet chemotherapy in metastatic lung squamous cell carcinomas. The Phase III CheckMate 017 showed overall survival improvement with Nivolumab when compared to docetaxel in second line treatment (9.2 months vs. 6 months, $p = 0.00025$, HR 0.59) and with a better safety. A planned subgroup exploratory analysis showed no difference in efficacy of nivolumab when compared to chemotherapy depending on PDL-1 tumor expression (Brahmer, july 9 NEJM 2015). The CheckMate 057 phase III study showed similar overall survival improvement in non-squamous NSCLC treated by nivolumab compared to docetaxel in 2nd line treatment (12.2 months vs. 9.4 months, $p = 0.0015$, OR: 0.73). However, in this study in a preplanned subgroup analysis, efficacy was similar between the two treatments when the threshold of PDL-1 expression was <1% (Borghaei NEJM 2015 373:1627). The prognostic and predictive role in the expression of PDL1 will have to be clarified by further studies (Barbee Annals of pharmacotherapy, august 17, 2015).

1.2 Immunotherapy in patient living with HIV/AIDS

Immune Checkpoints inhibitors administration is an efficient and innovative treatment in the general population with lung cancer. However, other populations, such as PLWHIV (People Living With HIV), may well benefit from anti-PD1 therapy, but no specific studies have been realized. It is indeed essential to conduct studies dedicated to PLWHIV with non small cell lung cancer (NSCLC) as:

- NSCLC is the most common of non-AIDS-related malignancy (Lanoy E Int j Cancer 2011);and represents the leading cause of cancer-related death among PLWHIV (Morlat AIDS 2014)
- Some studies have shown that NSCLC prognosis is worse among PLWHIV (Sigel BJC 2013, Suneja AIDS 2013; Coghill JCO 2015); thus any therapeutic innovation in the general population must be applied quickly to PLWHIV population taking into account its specificities;
- IFCT-1001 CHIVA phase II trial study of carboplatin plus pemetrexed followed by pemetrexed as first-line therapy for HIV infected patients with advanced non-squamous NSCLC was effective and reasonably well-tolerated, but the poor median overall survival

(7.6 months) suggested urgent unmet needs for investigations of others therapies than chemotherapy (Lavole Abst9076 ASCO 2016)

- Toxicity profile is better with nivolumab than docetaxel with 7-10% vs 54-71% grade 3-4 events (Borghaei NEJM 2015; Brahmer NEJM 2015)

- Oncological cytotoxic treatments and antiretrovirals (ARV) can cause interactions because of common CYP450 metabolism, or additive adverse events, thus increasing incidence of haematological, hepatic and renal toxicities, (Makinson, JTO 2010 and 2011). By contrast, nivolumab is a monoclonal antibody and does not have hepatic metabolism and therefore probably won't show interactions with antiretrovirals;

- Oncogene addiction is rare in PLWHIV with NSCLC (Crequit Lung cancer 2015) due to the almost constant smoking status of the study population. Therefore, the use of specific inhibitors is exceptionally an option; by contrast nivolumab has showed an efficacy in smoking populations (Borghaei NEJM 2015; Brahmer NEJM 2015).

- Standard chemotherapy reduces the number of CD4 altering the immunity of HIV patients.

- Strong evidence suggests that blocking the PD-1/PD-L1 axis with monoclonal antibodies could be of highest interest during HIV-associated NSCLC in order to 1°/ restore the HIV-specific T cell responses for potential effect on the HIV reservoir and HIV replication, together with antiretroviral therapies. (Trautmann Nat Med 2006 Nature Day 2006, Velu Nature 2009, Palmer J Immunol 2013) alongside ARVs and 2°/ thus contribute to the control of inflammation induced by HIV. Also, the high PD-1 expression levels on circulating CD8 during HIV infection (Day Nature 2006) suggests that blocking the PD-1/PD-L1 axis could restore tumor-specific cytotoxic T lymphocytes (CTL) functions - as much as in patients seronegative for HIV.

- A phase I-II study of escalating doses of nivolumab in 47 patients with hepatocellular carcinoma, carriers of hepatitis B or C, showed a good toxicity profile and a sustainable response, which suggests the safety of this molecule in a given virological context (El Khoueriry ASCO 2015, abst LBA101).

- To our knowledge, an ongoing phase I study is evaluating the association of nivolumab and ipilimumab in solid tumors including PLWHIV with lung cancer (NCT02408861), and another phase I study is evaluating pembrolizumab in PLWHIV with relapsed, refractory, or disseminated malignant neoplasms including lung cancer (NCT02595866).

- Therapeutic strategy is challenging in patients with advanced NSCLC and a poor performance status (PS \geq 2). In general PS is rather a prognostic factor than a predictive factor. Moreover, cytotoxic chemotherapy (particularly later lines of therapy) is associated with substantial toxicities, impaired quality of life, and a short lifespan in patients with a PS \geq 2. By contrast, immune checkpoint inhibitors (ICIs), particularly anti-PD1/PD-L1 monotherapy, often have favorable toxicity profiles, even in patients with a poor PS (Johnson DB et al. Cancer June 1, 2017). There is very little published experience to guide oncologists in terms of whether to use ICIs in patients with a poor PS. One phase II study with atezolizumab in cisplatin-ineligible patients with urothelial carcinoma reported a response rate of 25% for patients with a PS=2 (vs 23% for all patients) (Balar AV et al, Lancet. 2017;389:67-76). In the French cohort IFCT CLINIVO (Girard N et al ESMO 2017) for treatment of advanced non-small cell lung cancer (NSCLC) by nivolumab reporting the efficacy/toxicity of more than 900 patients included in the ATU of Nivolumab in France, more than 70% of patients were treated in third line setting or more and 20% had a PS \geq 2. In this large cohort of fragilized patients, overall survival and progression free survival were similar to that reported in phase III trial including only highly selected patients. Moreover, phase II trial has been projected by the IFCT to evaluate ICIs in PS \geq 2 patients, however HIV patients will be excluded, as usual. On the other hand, docetaxel - the standard of care previously proposed before the era of ICIs, is associated in HIV patients with substantial toxicities additive to that of anti-retrovirals and with an increased risk of pharmacological interactions. Moreover, results of the phase II CHIVA1 trial (Lavolé A et al ASCO 2016) has shown that chemotherapy by carboplatin plus pemetrexed provides a poorer results than in the general population. Altogether, these findings suggest that HIV patients with advanced NSCLC should not be excluded for CHIVA2 phase II trial in case of PS2, although statistical analysis will be analyzed by subgroups. Finally, it is important that HIV patients can benefit from therapeutic innovations in the field of NSCLC. HIV-NSCLC population is inherently of poor prognosis and patients excluded from therapeutic trials. Moreover, it is also important that this access is secured by the administration of ICIs in the context of a therapeutic trial, such as CHIVA 2.

1.3 Evaluation of risk-benefit ratio

Two Phase III trials showed superiority in terms of efficacy and tolerance of nivolumab in second-line treatment compared to docetaxel in metastatic NSCLC in the general population, so it is important to evaluate this treatment in PLWHIV in maximum security conditions, taking into account their specificities and complex underlying immunological status. As NSCLC in PLWHIV is a rare tumour, a phase 2 trial, using DCR data, would be

able to recruit a sufficient number of patients, in a reasonable period of time, to provide a proof of concept of the safety and efficacy of nivolumab in this population. Therefore, we think that an open-label, one arm phase 2 trial, with a rapid accrual, would be currently a crucial approach and a window of opportunity to explore whether nivolumab could find its place in PLWHIV with NSCLC. Such a trial is typically a trial for an academic sponsor, experienced in PLWHIV with NSCLC, which previously showed its ability to recruit patients with such a rare disease as the IFCT did with the IFCT1001-CHIVA trial, testing carboplatin plus pemetrexed followed by pemetrexed.

2 OBJECTIVES AND ENDPOINTS

2.1 Primary objective/endpoints

- Efficacy of the anti-PD1 antibody (nivolumab) as measured by DCR.

2.2 Secondary objectives/endpoints

- tolerance: Adverse Events (AEs) grade (NCI-CTC 4.0),
- impact on HIV control and immunological (CD4, CD8, HIV viral load each evaluation), other associated chronic infection susceptible of reactivation (HHV8, CMV, EBV, tuberculosis) and potential occurrence of autoimmunity (organ specific i.e. thyroiditis, adrenalitis and hypophysitis, or non organ specific)
- duration of response
- Responses rate according to tissue PD-L1 expression
- progression-free survival
- Overall survival
- Quality of life (LCSS)

2.3 Exploratory objectives / endpoints

- Monitor HIV, CMV, EBV, HBV, HCV, HHV-8-specific T cell responses in PBMC under anti PD-1 therapy: quantification, polyfunctionality, expression of immune check points
- Monitor the HIV reservoirs (HIV-DNA) and the residual HIV replication by ultrasensitive viral load, as well as EBV, CMV, HBV, HCV, HHV-8 viral load
- Monitor T cell activation/ exhaustion/differentiation and immune check point expression by flow cytometry and ultrasensitive cytokine/chemokine plasma measurements. Explore the tumor somatic mutanome by RNA sequencing on paraffin initial biopsy or fresh new biopsy by studying normal tissue in parallel

before treatment in order to characterize neoepitopes; if normal tissue not available, explore somatic tumoral mutations by comparing whole tumor exome sequencing with whole PBMC exome sequencing; further characterization of neo-epitope specific T cells in PBMC : polyfunctionality, expression of immune check points.

- Description of gene mutation that appear to be crucial for the response to immunotherapy or for adverse effects of immunotherapy, in particular MHC genes
- Immune monitoring of adverse effects: T cell phenotyping, cytokine/chemokine measurements, antibody dosage, auto-antibody dosage.
- Describe the tumoral microenvironment of NSCLC before nivolumab exposure (CD4, CD8, CD3 infiltrate, PD-1, PD-L1 expression).

This will be done on a special 68 mL blood sample that will be done on C1, C2, C3, C9, C15, C27, C51, end of treatment and in case of immune related adverse event. This will also be done on initial FFPE biopsies that will be repatriated from the different centers.

3 REGIMEN

Thirty eligible patients, previously treated by at least one line of platinum-based chemotherapy, will be included.

[figure not shown]
TREATMENT:

Nivolumab is administered intravenously (IV), over 30 minutes at 3 mg/kg every 2 weeks, until disease progression, death, limiting toxicity or patient refusal.

Premedication is not required.

Patients with tumoral progression will stop the treatment but will have a follow-up for the secondary endpoints of OS, and the toxicities assessment till a last study visit 4 weeks (\pm 1 week) after the last injection of the drug.

Twenty centers will be opened.

Schedule of the study design.

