8.2 Evaluation after protocol treatment

	Investigations	Timing
History and Physical Exam including:	
 physical examination including, pulse, blood pressure, weight performance status 	Within 30 days following last treatment day
Hematology	
 CBC including haemoglobin, differential, platelet count 	Within 30 days following last treatment day
Biochemistry	
 AST (SGOT) and ALT (SGPT) alkaline phosphatase bilirubin albumin creatinine lipase (and amylase if abnormal lipase) fasting glucose K, Cl, Na, Ca 	Within 30 days following last treatment day
	
 TSH (T3, T4 if TSH abnormal) 	As clinically indicated
Radiology*	
 CT-scan of chest and upper abdomen 	Every 8 weeks
Other	
 ECG 	As clinically indicated

Investigations	
• lung function tests: FEV1, FVC, TLCO and blood gas at room atmosphere	As clinically indicated
Adverse Events	Patients must be evaluated for treatment related adverse events until resolution	

* Only for patients who have not yet discontinued the study treatment

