11 SAFETY

11.1 Definition of Adverse Events

The term adverse event covers any unfavorable and unintended sign, symptom, syndrome, or illness that develops or worsens during the period of observation in the clinical study, reported for 100 days (3 months) post last treatment.

Clinically relevant abnormal results of diagnostic procedures including abnormal laboratory findings (e.g., requiring unscheduled diagnostic procedures or treatment measures, or resulting in withdrawal from the study) are considered to be adverse events.

Worsening of a sign or symptom of the condition under treatment will normally be measured by efficacy parameters. However, if the outcome fulfills the definition of “serious adverse event”, it must be recorded as such.

The adverse event may be:

- A new illness
- Worsening of a concomitant illness
- An effect of the study medication, including comparator
- A combination of two or more of these factors

No causal relationship with the study medication or with the clinical study itself is implied by the use of the term “adverse event”.

Adverse events fall into the categories “non serious” and “serious”.

Surgical procedures themselves are not adverse events; they are therapeutic measures for conditions that require surgery. The condition for which the surgery is required is an adverse event, if it occurs or is detected during the study period. Planned surgical measures permitted by the clinical study protocol and the condition(s) leading to these measures are not adverse events, if the condition(s) was (were) known before the start of study treatment. In the latter case the condition should be reported as medical history.

The following laboratory abnormalities should be documented and reported appropriately:

- Any laboratory test result that is clinically significant or meets the definition of an SAE
- Any laboratory abnormality that required the participant to have study drug discontinued or interrupted
- any laboratory abnormality that required the subject to receive specific corrective therapy.

It is expected that wherever possible, the clinical rather than laboratory term would be used by the reporting investigator (eg, anemia versus low hemoglobin value).

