- Medical/surgical admission other than to remedy ill health and planned prior to entry into the study. Appropriate documentation is required in these cases.
- Admission encountered for another life circumstance that carries no bearing on health status and requires no medical/surgical intervention (eg, lack of housing, economic inadequacy, caregiver respite, family circumstances, administrative reason).
- Admission for administration of anticancer therapy in the absence of any other SAEs (applies to oncology protocols)

Clarification of the difference in meaning between “severe” and “serious”

The term “severe” is often used to describe the intensity (severity) of a specific event (as in mild, moderate, or severe myocardial infarction); the event itself, however, may be of relatively minor medical significance (such as severe headache). This is not the same as “serious”, which is based on the outcome or action criteria usually associated with events that pose a threat to life or functioning. Seriousness (not severity) serves as a guide for defining regulatory reporting obligations.

SAEs/AEs will be reported up to 100 days (3 months) for both study drugs, and SAEs notification will be made within 24 hours.

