11.3 Period of Observation

For the purposes of this study, the period of observation for collection of adverse events extends from the date of signature of the informed consent until 100 days after the last day of study treatment except for adverse events related to study drug, which must be reported during follow-up period until resolution or initiation of further anti-tumor therapy.

If an Investigator detects a serious adverse event in a study subject after the end of the period of observation, and considers the event possibly related to prior study treatment,

he or she should contact the Sponsor to determine how the adverse event should be documented and reported.

At each visit/assessment AEs will be assessed from information collected from the source documents and information transcribed into the CRF.

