11.4 Documentation and Reporting of Adverse Events by Investigator

All adverse events that occur during the observation period set in this protocol must be documented on the pages provided in the case report form in accordance with the instructions for the completion of adverse event reports in clinical studies. These instructions are provided in the case report form itself.

The following approach will be taken for documentation:

- All adverse events (whether serious or non-serious, or considered as an alert term) must be documented on the “Adverse Event” page of the case report form.
- If the adverse event is serious, the investigator must complete, in addition to the “Adverse Event” page in the case report form, a “Serious Adverse Event/Expedited Report from a Clinical Trial” form at the time the serious adverse event is detected.

This form will be filled in the eCRF. In case of unavailability of the eCRF, a paper form will be sent by email to [contact].

Every attempt should be made to describe the adverse event in terms of a diagnosis. If a clear diagnosis has been made, individual signs and symptoms will not be recorded unless they represent atypical or extreme manifestations of the diagnosis, in which case they should be reported as separate events. If a clear diagnosis cannot be established, each sign and symptom must be recorded individually.

All patients who have adverse events, whether considered associated with the use of the investigational products or not, must be monitored to determine the outcome. The clinical course of the adverse event will be followed up according to accepted standards of medical practice, even after the end of the period of observation, until a satisfactory explanation is found or the investigator considers it medically justifiable to terminate follow-up. All questions on the completion and supply of adverse event report forms and any further forms issued to the investigator at a later date to clarify unresolved issues should be addressed to the IFCT.

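### For patients who progress, section 3 ends toxicity assessment about 4 weeks after the last injection, against 100 days in section 11; separately, routine HIV tests have no time point after the last infusion

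*Protocol*

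**What the plan says.** **Toxicity follow-up.** Section 3 states that patients with tumour progression stop treatment and are then followed for survival and for "the toxicities assessment till a last study visit 4 weeks" (± 1 week) after the last injection.

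Section 11 is longer and makes no exception for progression. Section 11.1 has adverse events "reported for 100 days (3 months) post last treatment", section 11.2 repeats the 100 days, and section 11.3 runs the period of observation from consent "until 100 days after the last day of study treatment". Section 11.3 carries drug-related events further, until they resolve or new antitumour treatment begins. Section 11.4 adds: "All adverse events that occur during the observation period set in this protocol must be documented".

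The post-treatment table in section 8.2 words it a third way: "Patients must be evaluated for treatment related adverse events until resolution". Its examination and laboratory rows are timed "Within 30 days following last treatment day".

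**HIV monitoring.** Section 2.2 lists the impact on HIV control (CD4, CD8 and HIV viral load at each evaluation) as a secondary endpoint. Section 13.5 asks the Data Monitoring Committee (DMC) to look for rising HIV viral load and falling CD4 counts. The table in section 8.1 places both tests before every infusion, until the patient is off protocol therapy. The table in section 8.2 has no immunovirology row. Sections 2.3 and 14.1 plan an exploratory 68 mL blood sample, including one at the end of treatment and one at any immune-related event.

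**The concern.** A site that follows section 3 would close toxicity assessment for a progressing patient at the 4-week visit. A site that follows section 11 would continue to day 100. Treatment continues until progression unless something else stops it, so progression should be a common reason for stopping, and the conflict is not confined to rare cases. Tolerance is the first secondary endpoint listed. If the collection window depends on the site, or on why the patient stopped, late events are captured unevenly.

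The HIV point is different in kind. HIV control is the question specific to this population and the DMC's named signal, yet the routine tests stop with the last infusion. Any change after it is not measured by those tests on schedule, including in a patient who stops early.

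**Working it through.** No sample-size, power or alpha figure enters this point, so there is no plan calculation to reproduce. The check is day arithmetic and a row-by-row reading of the assessment tables.

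**1. Toxicity windows**

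Inputs: 4 weeks ± 1 week (section 3); 100 days (sections 11.1 to 11.3); visit within 30 days (section 8.2).

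- Section 3 end point: 7 × 3 = 21, 7 × 4 = 28, 7 × 5 = 35, so day 21 to 35 (nominal 28).
- Days inside the section 11 window but after the section 3 end point: 100 − 35 = 65 to 100 − 21 = 79 (nominal 100 − 28 = 72).
- If the same visit must also meet the 30-day limit of section 8.2, it falls on day 21 to 30, and the difference is 100 − 30 = 70 to 79 days.

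Dated contacts after day 35:

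- Section 11.3 ties assessment to visits: "At each visit/assessment AEs will be assessed from information collected from the source documents".
- The section 8.2 examination and laboratory rows end by day 30.
- The 8-weekly CT in section 8.2 is footnoted as applying only to patients who have not discontinued. That is an odd footnote for a post-treatment table, but as written it supplies no contact for a patient who stopped at progression.
- Treatment-related events are followed until resolution. This follows known events and does not by itself prompt a search for new ones.
- Survival follow-up continues, without dates.
- The study-design schedule in section 3 is a figure that is not shown, so a later contact could appear there. It would not remove the conflict between the two texts.

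**2. Routine HIV viral load and CD4/CD8**

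Input: one draw before each infusion, every 2 weeks (sections 3 and 8.1). A patient with k infusions has k such values, of which k − 1 follow first exposure and 0 follow the last infusion.

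Taking section 13.5's 8 weeks as a window per patient that starts at the first infusion (an assumption), with infusions on schedule:

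| Infusions received | Values after first exposure | Last value | Weeks without a value, to week 8 |
|---|---|---|---|
| 1 (week 0) | 0 | week 0 | 8 − 0 = 8 |
| 2 (weeks 0, 2) | 1 | week 2 | 8 − 2 = 6 |
| 3 (weeks 0, 2, 4) | 2 | week 4 | 8 − 4 = 4 |
| 4 (weeks 0, 2, 4, 6), stopping at the 8-week CT | 3 | week 6 | 8 − 6 = 2 |

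The last row is the on-schedule case for a patient who stops at the first planned CT; the first three require stopping before it. If blood is drawn for a next infusion that is then cancelled, one further value exists 2 weeks after the last infusion.

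The exploratory sample covers residual HIV replication by ultrasensitive viral load, the HIV reservoir and T-cell phenotype. It is therefore an HIV measurement at end of treatment, but no section links it to the secondary endpoint or to DMC review, and it gives no routine CD4 count.

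**The case against.** **On toxicity.** Section 3 is a regimen summary, while section 11.3 is the section that defines the observation period and section 11.4 makes documentation mandatory within it. On that view section 3 merely dates the last on-site visit and reporting continues remotely. This is possible, but the section 3 sentence attaches the toxicity assessment itself to that visit, so the wording conflict stands. Section 11.3 also follows drug-related events past day 100, and section 11.4 follows any recorded event to a satisfactory outcome. Both protect follow-up of known events; neither finds new ones.

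A reader might infer that late events are excluded from the tolerance analysis, or that contact with patients ends at day 35. The documents support neither: section 11 keeps late events reportable, survival follow-up goes on, and the schedule figure cannot be read. A reader might also take section 8.2 as limiting collection to treatment-related events. It is silent on other events, but section 11.3 covers them.

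**On HIV tests.** Nothing here contradicts anything else. Section 2.2's reference to each evaluation promises no post-treatment value, section 12.4 continues laboratory studies during dose delays, patients are under experienced HIV care, and DMC procedures are left to a charter that is not shown. All of that stands, and it makes this an improvement rather than an error. It would be wrong to infer that HIV is unmeasured once treatment ends, given the exploratory sample, or that the DMC lacks most of its 8 weeks of data in general. The long gaps arise only when a patient stops after one to three infusions. What remains is that no routine time point is set after permanent discontinuation.

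**Conclusion.** **Toxicity window: wrong as written, minor.** Section 3 and section 11 give different ends to toxicity assessment for patients who progress, 65 to 79 days apart. The consequence is possible under-capture of late events for the tolerance endpoint, at sites that follow section 3 or that have no later prompt to ask. That no dated contact follows about day 35 rests on the text alone.

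**HIV tests: an optional improvement.** No routine HIV viral load or CD4/CD8 value is scheduled after the last infusion. A patient who stops after one infusion has no scheduled routine value after exposure; one who stops at the 8-week CT after four infusions has a last value at week 6. These figures assume on-schedule dosing from week 0.

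The number of patients affected by either point cannot be estimated from the protocol. Neither point touches the primary endpoint, sample size, alpha or power.

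**What to change.** 1. Reconcile sections 3, 8.2 and 11.3 so that one adverse-event collection window applies whatever the reason for stopping. State in section 8.2 how its treatment-related row relates to collection of all events in that window.
2. Add one dated adverse-event contact, for example by telephone, at the end of the window.
3. As an improvement, add routine HIV viral load and CD4/CD8 to the end-of-treatment draw and to the visit within 30 days, both already planned.

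Cost: a short wording amendment, one telephone contact per patient, and one or two sets of standard HIV tests per patient on existing blood draws.
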